12.3.7 Baseline Characteristics

Demographic (e.g. age and race) and relevant medical data (e.g. cancer diagnosis, treatment history, pre-existing co-morbidities) will be collected at the baseline visit. The study team member will obtain information necessary to complete these forms from the subject's electronic medical records when the subject is unable to provide this information in sufficient detail (e.g., staging, surgical procedures, types and doses of treatments).

13.0. CONFIDENTIALITY OF DATA AND DATA STORAGE

13.1 Utilizing Carevive Software for Symptom Monitoring.

Several steps will be taken to ensure that participant confidentiality is maintained throughout the study to the best of our ability. Patient reported symptom data will be collected via a Carevive software which complies completely with HIPAA standards. No Carevive software will be loaded on to cancer center devices. The Carevive platform will run in a web browser using Secure Sockets Layer (SSL) for managing the security of message transmissions over the Internet.

All questionnaires will be de-identified and reflect only the study-specific identification number of the participant. All self-reported questionnaires will be administered electronically using the Research Electronic Data Capture (REDCap) system.

13.2 Utilizing Research Electronic Data Capture (REDCap) and Information for Integrating Biology and the Bedside (i2b2)

Quality of life data will primarily be collected electronically via a web-based survey administered using Research Electronic Data Capture (REDCap) software. REDCap is a secure, web-based application for building and managing online surveys and databases and is made available free of cost through the University of Rochester Clinical Translational Science Institute. All data forms will be checked immediately by the REDCap system as they are being completed by the study participant to ensure completeness (i.e., that no question was skipped unintentionally), and a pop-up message feature will be used to encourage a response. Once data collection is complete, REDCap provides an automated export procedure for data download. Every effort will be made to reduce attrition and obtain follow-up data. Steps will be taken to avoid missing data, including careful instructions, and offering assistance.

Informatics for Integrating Biology and the Bedside (i2b2) will be used to help extract data from the electronic medical records. Specifically it will collect physician CTCAE ratings. The i2b2 clinical data query tool is made freely available to researchers at the University of Rochester (UR) through the leadership of the Clinical and Translational Science Institute (CTSI) and the UR Medical Center Information Systems Division. i2b2 is an open source informatics framework developed by the NIH-funded i2b2 Center at Harvard University to enable researchers to query clinical data from multiple clinical systems for research purposes. Through an easy-to-use graphical user interface, the i2b2 tool has the ability to perform a variety of queries for the purposes of cohort identification to support study feasibility, volunteer subject recruitment, and data visualization. Some examples of data currently available include patient demographics, diagnoses, medications, procedures, providers, laboratory results, microbiology results, patient questionnaires, and social history. De-identified data is available for study feasibility assessment and planning. With proper IRB approvals, users may

request identified data in the form of a user-specific i2b2 project, which can be exported for analysis.

The University of Rochester has developed a complementary tool to automate the process of moving clinical information from i2b2 to REDCap using an innovative graphical user interface. Researchers may use the tool to map clinical data in i2b2 to specific fields in a REDCap project using an application programming interface (API). With proper human subject approvals, identifiable information is available. Once in REDCap, information may be manipulated further, combined with other data collected outside the electronic health record system, and exported for analysis.

13.3. Data Storage

All hardcopy research records will be stored onsite in the University of Rochester Medical Center, in the Cancer Control Unit of the James P. Wilmot Cancer Institute, in an office suite secured by electronic key cards. Offices within the unit are again secured by key and data is kept in locked file cabinets. Electronic research records are stored on the University of Rochester Medical Center's password secured and firewall protected networks. These are the same methods of security used for patient medical records. All study data will be kept for a period of at least 6 years after the study and all reports and publications are complete. Carevive's electronic records will be compiled on their secure server for the duration of the study and transferred to the University of Rochester on completion of the study. They would only retain de-identified data on their server after the close of the study.

13.4. Assignment of Study ID

The study team will assign a numerical Study ID to each participant once they have agreed to participate in the study. Study forms and questionnaires will use this number and the participant's first and last initials as identifiers to ensure data integrity. Other identifying information will not exist on these forms. A complete list of study participants with study ID, name, and contact information will be maintained separately for the purpose of contacting participants if necessary; this database will be maintained until the study is closed. This linkage information will only be accessible to the study chair, study investigators, and the individual responsible for maintaining the database.

14.0. RESEARCH INFORMATION IN MEDICAL RECORDS

Documentation of study participation will be included in the medical record by means of uploading a signed consent form to each cancer survivor's medical record, for those participants enrolled in the research study from Wilmot Cancer Institute/University of Rochester Medical Center. Additionally, the subject's CTCAE results will be recorded in the chart at their visit approximately every 3 months. No further research-related information will be included in the medical record.

15.0. DATA ANALYSIS AND MONITORING

15.1 Primary Outcomes:

Primary Aim 1: *To evaluate the feasibility and usability of symptom monitoring and management with Carevive software.* Specifically, we will determine the demand for this intervention by calculating the rate of compliance. For example, in the case of monthly compliance, the

proportion of subjects who log in at least once during this time frame will be reported. The threshold criteria for compliance based on previous studies [29-30], will be a monthly compliance of 75% (ie. during each month, an average of at least 75% of the subjects completed at least one Carevive survey). Compliance will be determined for both survey completion and access of generated care plans. A sample size of 50 subjects produces a two-sided 95% confidence interval with a width of 0.254 for a point estimate of 75% compliance. Separately patient-level compliance will be determined, based on the proportion of logins that the subject completed during the course of the study. Reasons for noncompliance will be elicited at their subsequent login and will be reported descriptively.

Patient-rated usability, based on their SUS survey results, will also be employed as a measure of feasibility. This survey will be administered to subjects at the end of the study. A Score of >68 indicates greater than average usability [25]. We will determine overall mean usability scores, and we can produce a 95% confidence interval for the mean with a width of 0.57 standard deviations, utilizing the sample of 50 subjects.

We will also determine potential implementation obstacles for Carevive software by asking patients who fail to consent to the study to provide their reasoning. This will be reported descriptively. We will also keep track of the proportion of patients who are approached who fail to consent.

15.2 Secondary Outcomes:

Primary Aim 2: *To determine how patient-reported toxicities correlate to the subject's quality of life, distress level, drug adherence, health care utilization and physician reported toxicities.* Grading of each symptom and numeric values for quality of life, distress level, drug adherence and health care utilization rate will be determined as described in the "Data Collection and Monitoring Section." The strength of the association between symptom grade and each outcome will be measured using the Spearman's rank correlation coefficient.

Week		0	1	2	3	4	5	6	7	8	9	10	11	12	14	16	18	20	22	24	26	28	30	32	34	36	38	40	42	44	46	48	Treat ment D/C	
PR- Symptoms	PRO-CTCAE Carevive survey	X	X	X	X	X	X	X	X	X	X	X	X	X	X	X	X	X	X	X	X	X	X	X	X	X	X	X	X	X	X	X		
PR- Healthcare Utilization	Carevive survey 7s					X				X				X		X		X		X		X		X		X		X		X		X		
PR- Drug Adherence	Adherence 7s Carevive survey					X				X				X		X		X		X		X		X		X		X		X		X		
Software Utilization	Carevive collected data		X	X	X	X	X	X	X	X	X	X	X	X	X	X	X	X	X	X	X	X	X	X	X	X	X	X	X	X	X	X	X	
Care plan Utilization	Carevive collected data		X	X	X	X	X	X	X	X	X	X	X	X	X	X	X	X	X	X	X	X	X	X	X	X	X	X	X	X	X	X	X	
Consent Failure	Recorded on screening log	X																																
Quality of Life	FKSI-DRS in office	X												X					X							X						X		
Distress Score	Distress Thermomer in office	X												X					X							X						X		
Usability	SUS																															X	X	
CD- Symptoms	CTCAE	X												X					X							X						X		
CD- Healthcare Utilization	Electronic Medical Record																															X	X	
CD- Drug Adherence	Pharmacy Confirmed																															X	X	

Abbreviation: CD = Clinician Determined, PR = Patient Reported, PRO = Patient Reported Outcomes, CTCAE = Common Terminology Criteria for Adverse Events, FKSI-DRS = Functional Assessment of Cancer Therapy: Kidney Symptom Index- Disease related Symptoms, SUS = System Usability Scale

REFERENCES

1. National Cancer Institute. Bethesda, M., . *SEER Cancer Statistics Factsheets: Kidney and Renal Pelvis Cancer*. 2016.
2. National Cancer Institute. Bethesda, M., . *Kidney Cancer (adult) -- renal cell carcinoma*. . 2016, NCI.
3. Fellner, C., *Launch of Breakthrough Therapies Will Reshape Renal Cell Carcinoma Market*. P T, 2016. **41**(8): p. 523-5.
4. Hartmann, J.T. and C. Bokemeyer, *Chemotherapy for renal cell carcinoma*. Anticancer Res, 1999. **19**(2C): p. 1541-3.
5. Cella, D. and J.L. Beaumont, *Pazopanib in the treatment of advanced renal cell carcinoma*. Ther Adv Urol, 2016. **8**(1): p. 61-9.
6. Motzer, R.J., et al., *Overall survival in renal-cell carcinoma with pazopanib versus sunitinib*. N Engl J Med, 2014. **370**(18): p. 1769-70.
7. Klapper, J.A., et al., *High-dose interleukin-2 for the treatment of metastatic renal cell carcinoma : a retrospective analysis of response and survival in patients treated in the surgery branch at the National Cancer Institute between 1986 and 2006*. Cancer, 2008. **113**(2): p. 293-301.

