2.3. Secondary Aim

2.3.1. Collect preliminary data on RCC patients' symptoms, health care utilization, quality of life, distress level and oral drug adherence while on targeted therapy or immunotherapy.

- To determine how patients' treatment-related toxicities correlate to their quality of life, distress level, drug adherence and health care utilization.

3.0.CHARACTERISTICS OF THE RESEARCH POPULATION

3.1 Number of Subjects: We expect to recruit 50 advanced renal cell carcinoma patients from the genitourinary oncology program at Wilmot Cancer Institute of the University of Rochester Medical Center over a one-year period.

3.2 Gender of Subjects: Both men and women will be enrolled in this study. Advanced RCC is known to be almost twice as prevalent in men than women [24], therefore we can expect a roughly 2:1 male to female enrollment rate.

3.3 Age of Subjects: We will recruit patients 18 years and older for this study, however RCC is very uncommon in patients <45 years of age and typically affects adults between the ages of 45 and 84 [1].

3.4 Racial and Ethnic Origin: This study has no enrollment restrictions based upon race or ethnic origin. RCC is known to be less prevalent in Asian and Pacific Islanders [1].

3.5 Inclusion Criteria:

- 3.5.1 Diagnosis of histologically confirmed renal cell carcinoma of any subtype with either pathological or radiographic evidence of metastatic disease
- 3.5.2 Greater than 18 years of age
- 3.5.3 A participating Wilmot Cancer Center oncologist has determined that candidate should be started on either oral targeted therapy or immunotherapy for treatment of their advanced RCC; this can be for first-line or any subsequent line therapy**
- 3.5.4 Able to provide written informed consent
- 3.5.5 Proficient in the English language and self-reports as literate
- 3.5.6 Must have an active email address or access to a smart device

3.6 Exclusion Criteria:

- 3.6.1 Women cannot be breast-feeding
- 3.6.2 Does not have regular access to the internet
- 3.6.3 Unable to come to the Wilmot Cancer Center for appointments every 3-4 months for routine visits with their primary oncologist
- 3.6.4 Subjects who were on the study previously will not be allowed to re-enroll in the event of a treatment change

3.7 Vulnerable Subjects: No special classes of subjects such as fetuses, neonates, children, pregnant women, prisoners, institutionalized individuals or other vulnerable populations will be recruited.

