6.0. METHODS AND STUDY PROCEDURES

6.1 Overview of Study:

We will conduct a phase II, single-arm clinical trial to assess the feasibility of reporting and managing side effects from oral targeted therapy or immunotherapy, through Carevive software, in patients who have advanced RCC. The study will begin when the consented subject starts a new therapy, either an oral targeted agent (pazopanib, sunitinib, axitinib, cabozantinib, lenvatinib, everolimus) or infusional immunotherapy (nivolumab), and will continue for a duration of 48 weeks or until drug is permanently discontinued by their primary oncologist. All study subjects will be asked to log their symptoms through Carevive software weekly for 12 weeks and then every other week for the next 36 weeks. Based on their symptoms, subjects will receive self-management instructions through the software (if applicable). Subjects will also be asked to monitor their medication compliance and health care utilization through the Carevive software once every four weeks for the length of the study. In addition, subjects will be asked to fill out a survey at their medical oncology office visits approximately every 3 months. This survey will include a distress assessment and a quality of life questionnaire. During these visits, a clinician will formally assess the subject's medication related adverse events. At the end of the study, the subject will be asked to fill out an in-office survey rating the usability of the Carevive software. On study completion, the subject's electronic medical record will be reviewed to determine health care utilization and oral targeted therapy refill history during the study period.

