12.1.2 Reasons Participants Do Not Complete Survey or Utilize Care Plans

At the following login, subject will be asked the reason they did not login in the previous time point/time points (if applicable) and why they did not access the care plan.

12.1.3 Software Usability Scoring:

At the 48 week time point or at the point of subject withdrawal from study, they will be asked to take the System Usability Scale [25]. This is a 10 question survey where responses range from "Strongly Disagree" to "Strongly Agree," which are ranked with corresponding numbers. The survey provides us with a score of between 0 and 40 which is then multiplied by 2.5 to convert to a scale of 0 to 100. A SUS score above a 68 would be considered above average and anything below 68 is below average [25].

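### The usability score (SUS) is collected once, in the office, at exit, with no remote route and no earlier score; subjects who leave without an office contact give none, and the stated precision assumes that all 50 respond

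*Combined protocol and SAP*

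**What the plan says.** Section 2.2.1 makes patient-reported usability the acceptability component of the primary aim, and section 15.1 uses the SUS results as a measure of feasibility.

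- **Timing.** Section 15.1: "This survey will be administered to subjects at the end of the study". Section 12.1.3 is fuller: "At the 48 week time point or at the point of subject withdrawal from study". Section 6.7 agrees with 12.1.3. The schedule marks SUS at week 48 and at treatment discontinuation and nowhere else.
- **Place.** Section 6.1: "At the end of the study, the subject will be asked to fill out an in-office survey rating the usability of the Carevive software". Section 6.7 specifies a tablet.
- **Benchmark.** Section 15.1: "A Score of >68 indicates greater than average usability".
- **Precision.** Section 15.1 promises a "95% confidence interval for the mean with a width of 0.57 standard deviations, utilizing the sample of 50 subjects". Section 3.1 gives the enrolment target: "We expect to recruit 50 advanced renal cell carcinoma patients". The precision figure therefore counts a score from every enrolled subject.
- **Missing scores.** Section 13.2 lists steps to prevent missing data. No section states how many SUS scores are expected, how a missing one is analysed, or that the number obtained will be reported.

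**The concern.** With a single collection point that needs an office contact, a score missed at exit cannot be recovered. Participation ends at 48 weeks or when the drug is permanently stopped (section 6.1), and the population has metastatic cancer, so some exits will come through death, admission or refusal. Section 7.2 also allows withdrawal for non-compliance, so some early leavers may be people who had disengaged from the software. If the chance of giving a score is related to the experience of the software, the reported mean does not represent everyone enrolled, and a confidence interval does not reveal this.

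A second problem remains even with a complete response. One mean pools ratings given after a few weeks of use with ratings given after 48 weeks. A subject who stops logging in but stays on drug rates the software long after last using it.

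**Working it through.** **1. The plan's own figure.** Inputs from section 15.1: 95% interval, 50 subjects. Two-sided is implied.

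Width in SD units = 2 × t(0.975, n − 1) / √n = 2 × 2.0096 / 7.071 = 0.568. This matches the stated 0.57.

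**2. The same formula with fewer scores.** The documents give no rate of missing SUS, so the missing share is an assumption, shown over a range.

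| Scores obtained | Missing (assumed) | 95% CI width (SD) |
|---|---|---|
| 50 | 0% | 0.57 |
| 45 | 10% | 0.60 |
| 40 | 20% | 0.64 |
| 35 | 30% | 0.69 |
| 30 | 40% | 0.75 |
| 25 | 50% | 0.83 |

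**3. Possible bias.** Let f be the share without a score and D the mean of responders minus the mean that non-responders would have given. The mean in all enrolled is (1 − f) × responder mean + f × non-responder mean, so the observed mean exceeds it by f × D. Both inputs are assumed:

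- f = 0.20, D = 10 points: 0.20 × 10 = 2.0 points
- f = 0.30, D = 10 points: 0.30 × 10 = 3.0 points
- f = 0.30, D = 15 points: 0.30 × 15 = 4.5 points

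If D is zero there is no bias; if D is negative the observed mean is too low.

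**4. How different non-responders must be to matter.** Suppose the observed mean is 72 (assumed). The all-enrolled mean falls to 68 when non-responders average (68 − (1 − f) × 72) / f:

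- f = 0.20: (68 − 57.6) / 0.20 = 52
- f = 0.30: (68 − 50.4) / 0.30 = 58.7
- f = 0.40: (68 − 43.2) / 0.40 = 62

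**5. Which exits have a route to a score.** Section 6.6 schedules in-office assessments at weeks 12, 24, 36 and 48 only. In the treatment discontinuation column of the schedule, the other marked items come from software logs, the medical record or pharmacy confirmation. The quality of life, distress and CTCAE rows are not marked there. SUS is thus the one item in that column that the subject must answer, and no visit is defined for it.

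**6. Spread of exposure.** There are 12 weekly surveys and then 18 every other week (weeks 14 to 48), 30 after baseline. A subject who leaves at week 4 has been sent at most 4 of the 30; a completer has been sent all 30. At week 12, everyone still enrolled has been sent the same 12.

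**The case against.** A reader might infer from section 15.1 that only subjects who reach week 48 are scored, or that the mean comes mainly from those who stayed. The documents do not support this. Sections 6.7 and 12.1.3 and the schedule also ask for SUS at withdrawal or discontinuation, and the end of the study in section 15.1 can be read as each subject's own end.

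Nor does retention measure missing scores. With an assumed median drug duration of 26 to 48 weeks, 28% to 50% of subjects would still be on study at week 48, but stopping the drug is itself a trigger for SUS. If 20% to 30% of scores were missing, all from early leavers, completers would supply 28/80 to 28/70 (35% to 40%) of scores at the shorter median and 50/80 to 50/70 (63% to 71%) at the longer. Whether completers form the majority cannot be settled.

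The exit route is also more workable than the schedule alone suggests. Permanent discontinuation is the oncologist's decision (section 6.1), people unable to attend every 3 to 4 months are excluded (3.6.3), staff telephone those who miss two logins (6.5), and contact details are kept (13.4). Death or a treatment change need not reflect a poor experience of the software. The value 68 is an interpretive benchmark; no test or success rule depends on it. Rating the software at the end of use is a legitimate choice for a 48-week programme.

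All of this stands. It leaves four gaps: no remote route for SUS, no earlier score, no rule for a missing score, and a precision figure that needs all 50.

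**Conclusion.** The point holds as a cheap improvement. The SUS mean will come only from subjects who complete the survey at an exit contact, and the plan neither allows for missing scores nor offers another way to obtain them. The width of 0.57 SD is right for 50 scores and only for 50; with 40 or 35 it is 0.64 or 0.69 SD. That loss of precision is modest.

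Bias is possible, at 2.0 to 4.5 points under the assumed combinations of 20% missing with a 10-point difference and 30% missing with a 15-point difference. A reader might infer that the mean is certainly too high, or that a usability conclusion would be reversed. Neither follows: the missing share, the score difference and its sign are not in the documents, and no decision rule rests on 68. The mixing of short and long exposure, by contrast, follows directly from the design whenever subjects leave at different times.

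**What to change.** 1. In sections 6.7 and 12.1.3, allow the exit SUS to be completed through a REDCap web link when the subject does not return to the office. REDCap web surveys are already in use (section 13.2), and eligibility already requires email or a smart device and regular internet access.
2. Add the ten-item SUS to the week 12 in-office assessment (section 6.6 and the schedule), where subjects already complete quality of life and distress questionnaires on a tablet or computer. Keep the week 48/exit score as the planned result. Report the week 12 score as a supplementary result at near-equal exposure, and use it in a sensitivity analysis for subjects with no exit score.
3. In section 15.1, state that the number of SUS scores obtained will be reported with the mean and its actual 95% confidence interval, and align the timing with sections 6.7 and 12.1.3 and the schedule.

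The cost is a few lines of text, one survey link, and ten extra items at one visit. The changes reduce the problem without removing it: a subject who dies or is lost before week 12 without an exit contact still has no score, and routine visits every 3 to 4 months will not all fall exactly at week 12.

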1.5 PRO-CTCAE

The National Cancer Institute's Common Terminology Criteria for Adverse Events (CTCAE) is a tool designed to standardize the reporting of clinician reported adverse events (AE) during clinical trial. This exhaustive list of symptoms, physical findings, and lab abnormalities are graded using a severity scale [10]. Approximately 10% of the adverse events in the CTCAE are patient symptoms, which are conveyed from the patient to the clinician and then recorded. This second-hand method of AE reporting has been shown to be unreliable [22], with a physician tendency to under-rate patient symptoms [23]. To improve adverse event reporting, the National Cancer Institute (NCI) developed a patient-reported outcome supplement to the CTCAE, called PRO-CTCAE. PRO-CTCAE includes questions on 124 potential patient reported items. The patient directly completes the questions through either a computer interface or an automated telephone system, eliminating the need for information to pass through a clinician. Once further validation of this reliable questionnaire is done, it is intended to be used to monitor adverse events in clinical trials [10]. We will be using the format of PRO-CTCAE in our side effect surveys since it is an independently verified strategy for side effect monitoring. We will focus on the eleven common side effects listed in the previous section to prevent the surveys from being overly burdensome to our patients.

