1.6 Significance and Innovation of Study

Clinician-initiated grading of treatment side effects in cancer has previously been shown to be unreliable [23]. Our intention is to implement a software program to more accurately obtain patient side effect information and to provide patients with corresponding self-care plans. Oral targeted RCC therapies and immunotherapy carry significant side effects. The goal of this project is to generate and implement self-care plans that we believe will empower our patients to perform self-care in order to minimize treatment-related side effects between visits. These care plans will include basic side effect home management but will automatically trigger our staff pharmacists with severe side effects that need immediate personal assistance. To our knowledge, this is the first study seeking to validate an RCC-treatment specific, electronic side effect reporting tool. This strategy of AE monitoring and management via an automated self-care plan has the potential to enhance self-reporting, decrease unnecessary clinic visits and telephone calls and provide overall better patient care. Additionally, to our knowledge this is the first electronic reporting system that is collecting side effect data in the PRO-CTCAE format. Utilizing the PRO-CTCAE questions will enable this software to be more readily incorporated as a reporting tool in future clinical trials

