12.3 Secondary Study Outcome Measures

12.3.1 Patient Reported Toxicities

Patient reported toxicity data will be collected via Carevive surveys weekly for the first 12 weeks and then every other week for another 36 weeks. The questions will be from the PRO-CTCAE which is a patient-reported outcome measure developed to evaluate the toxicities that clinical trial subjects experience [10]. We will not deliver the PRO-CTCAE in its entirety but will specifically ask about the following common toxicities that are experienced with oral targeted therapy and immunotherapy: diarrhea, nausea, vomiting, fatigue, hand/foot syndrome, rash, abdominal pain, anorexia, mouth sores, cough and shortness of breath.

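### Section 15.2 compares patient and physician toxicity ratings by Spearman's rho only; a lower/equal/higher cross-tabulation beside it would show the direction of disagreement at little cost

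*Combined protocol and SAP*

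**What the plan says.** The analysis plan for the secondary outcomes (section 15.2) relates patient-reported toxicities to quality of life, distress, "drug adherence, health care utilization and physician reported toxicities". One method covers all of these: "The strength of the association between symptom grade and each outcome will be measured using the" Spearman coefficient. Neither that section nor any other names a paired difference, percentage agreement, kappa or patient-by-physician table.

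The aim in section 2.3 is narrower. It asks how "treatment-related toxicities correlate to their quality of life, distress level, drug adherence and health care utilization" and does not list physician grades.

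The two ratings come from different instruments. For patients (section 12.3.1), "The questions will be from the PRO-CTCAE which is a patient-reported outcome measure"; clinicians grade by CTCAE (section 12.3.2). Sections 6.4 to 6.6 schedule both at weeks 0, 12, 24, 36 and 48.

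The background explains the interest in comparing them. Section 1.5 calls second-hand adverse event reporting unreliable, "with a physician tendency to under-rate patient symptoms". Section 1.6 opens with "Clinician-initiated grading of treatment side effects in cancer has previously been shown to be unreliable", continues "Our intention is to implement a software program to more accurately obtain patient side effect information", and describes the study as seeking to validate the reporting tool.

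**The concern.** Quality of life, distress, adherence and utilization are different constructs from symptom grade, so a rank correlation is a reasonable summary for them. Physician grades are another matter: they cover largely the same symptoms at the same time points. With two raters of similar content, a reader will also want to know how often they disagree and which of them is lower.

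Rho answers neither question. A uniform downward shift in one rater leaves the ranks, and so rho, unchanged. At stake is the use made of paired data already being collected: as planned, they cannot bear on the under-rating mentioned in section 1.5, nor on whether patient reporting captures toxicity that clinician grading misses.

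**Working it through.** **Plan's own figures.** The plan gives no figure for this comparison. Its two precision figures in section 15.1 concern compliance and usability and play no part here. Both reproduce: an exact Clopper-Pearson interval at 37.5 of 50 runs from 0.607 to 0.862, width 0.254; and 2 × t(0.975, 49)/√50 = 0.568 SD, given as 0.57.

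**Step 1: invariance (no data assumption needed).** If the physician level equals the patient level minus a constant in every pair, the ranks are identical and rho = 1. Example with 50 pairs: patient grades 1/2/3/4 in counts 16/16/12/6, physician one lower throughout. Rho = 1.00, exact agreement 0%, mean difference −1.00. This requires every patient to be symptomatic.

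**Step 2: with a floor at 0 (assumed inputs).** Both raters are put on one 0–3 scale. Patient levels 0/1/2/3 occur at 40/30/20/10%, and the physician is one level lower with a floor at 0, giving physician levels 0/1/2 at 70/20/10%. The documents give neither the scale nor the distribution.

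- Mid-ranks as proportions: patient 0.20, 0.55, 0.80, 0.95; physician 0.35, 0.80, 0.95. Both have mean 0.50.
- Rank variance = (1 − Σp³)/12. Patient: (1 − 0.100)/12 = 0.075. Physician: (1 − 0.352)/12 = 0.054.
- Rank covariance = 0.4(−0.30)(−0.15) + 0.3(0.05)(−0.15) + 0.2(0.30)(0.30) + 0.1(0.45)(0.45) = 0.054.
- Rho = 0.054/√(0.075 × 0.054) = 0.849.

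**Step 3: other summaries of the same pairs.**

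- Physician lower: 30 + 20 + 10 = 60% of all pairs, and every pair with a symptomatic patient.
- Linear weighted kappa: observed disagreement 0.60; expected 0.16 + 0.24 + 0.32 + 0.26 = 0.98; kappa = 1 − 0.60/0.98 = 0.39.
- Quadratic weighted kappa: expected 0.24 + 0.24 + 0.60 + 0.72 = 1.80; kappa = 1 − 0.60/1.80 = 0.67.

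**Step 4: collapsed to absent/present.** Patients report the symptom in 60% of pairs, physicians in 30%. The physician is lower in 30% of all pairs, which is 30/60 = 50% of symptomatic pairs.

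**Step 5: with noise (assumed model).** In 4,000 simulated trials of 50 pairs (latent severity with mean 2.5 and SD 1, rater noise SD 0.5, rounded to grades 0–4), mean rho was 0.726 without under-rating and 0.725 with a one-grade latent under-rating. The mean physician-minus-patient difference moved from 0.00 to −0.92.

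Rho barely reacts to the shift, while the paired summaries do. Kappa falls below 1 but does not say which rater is lower, and its value depends on the weights. Only the lower/equal/higher split gives direction, and its size depends on the categories chosen (60% against 30% here).

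**The case against.** The strongest reply is that Spearman answers the question asked. Sections 2.3 and 15.2 both speak of correlation, and no aim sets out to estimate agreement or under-rating. A reader might infer that the plan uses the wrong method for its aim; the documents do not support that.

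A reader might also infer that under-rating is the whole case for the software. It appears once, in section 1.5, as background to the development of PRO-CTCAE. The unreliability cited in section 1.6 has no stated direction, and sections 1.1 and 1.6 offer other reasons, such as less face-to-face contact and support for self-care. Nor does any passage say that a high rho will be read as agreement; that misreading is possible but speculative.

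The two ratings are not strictly interchangeable. The diarrhea example in section 6.5 is worded by frequency, whereas section 1.5 describes CTCAE as a severity scale, so one level lower has no meaning until a mapping is chosen. Section 6.1 has the clinician assess events related to the medication, so a lower clinician grade may reflect attribution.

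All of this stands, and it limits the weight of the point. What remains is that section 15.2 itself brings in physician grades, and that rho alone cannot speak to the validation and accuracy language of section 1.6.

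**Conclusion.** This is a cheap improvement, not a statistical error. Rho should stay; alone, it cannot show whether clinicians record symptoms less often or as less severe than patients. That property needs no assumption.

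The figures do need assumptions. Rho 0.85 with 60% of pairs lower, kappa 0.39 or 0.67 according to the weights, and 30% lower after an absent/present collapse all rest on an assumed distribution and a common scale. They illustrate the gap and do not predict what this trial will find. The comparison is secondary and preliminary, and the primary feasibility outcome is unaffected.

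**What to change.** Keep Spearman's rho and add to section 15.2, for physician grades only:

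- **Symptoms.** Use those rated by both: abdominal pain, anorexia, cough, diarrhea, fatigue, mouth sores (oral mucositis), nausea, rash, shortness of breath and vomiting. Reconcile the clinician lists first: sections 6.4 and 6.6 omit hand/foot syndrome and add weight loss, while section 12.3.2 includes hand/foot syndrome. Add that symptom only if the reconciled list contains it.
- **Pairing.** Pair each CTCAE grade with the Carevive report at weeks 0, 12, 24, 36 and 48. State a window, since section 6.6 allows routine visits every 3–4 months.
- **Summary.** Cross-tabulate patient against physician on categories fixed before analysis: absent/present as the main one, lower/higher severity as the second. Report the percentage of pairs with the physician lower, equal or higher, with confidence intervals that resample subjects because each contributes several pairs.
- **Optional.** A weighted kappa, with its weights stated in advance.

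The cost is a per-symptom mapping, a pairing rule and a subject-level bootstrap, with no new visit, form or patient burden. The drawback is that results depend on the mapping and may partly reflect attribution to medication, so they should be labelled descriptive.
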